6.1.2 Adverse event start date

The algorithm only applies to event that has partial start date. Please note that **completely missing start dates** will not be imputed.

Note: Imputed dates will be used in the derivation of treatment emergent AEs and assignment of study periods. The actual partial dates will be reported in the listings.

The following matrix explains the logic behind the imputation.

	MON MISSING	MON < TRTM	MON = TRTM	MON > TRTM
YYYY < TRTY	(D) Before Treatment Start	(C) Before Treatment Start	(C) Before Treatment Start	(C) Before Treatment Start
YYYY = TRTY	(B) Uncertain	(C) Before Treatment Start	(A) Uncertain	(A) After Treatment Start
YYYY > TRTY	(E) After Treatment Start	(A) After Treatment Start	(A) After Treatment Start	(A) After Treatment Start

The following table is the legend to the logic matrix.

	Day	Month	Year
Partial Adverse Event Start Date	Not used	MON	YYYY
Treatment Start Date (TRTSTD)	Not used	TRTM	TRTY
Treatment in SP2 Start Date (TRT2STD)	Not used	TRT2M	TRT2Y
Relationship			
Before Treatment Start	Partial date indicates AE start date prior to Treatment Start Date		
After Treatment Start	Partial date indicates AE start date after Treatment Start Date		
Uncertain	Partial date insufficient to determine relationship of AE start date to Treatment Start Date		
Imputation Calculation			
NC / Blank	No convention		
(A)	MAX (01MONYYYY, TRTSTD)		
(B)	TRTSTD		
(C)	15MONYYYY		
(D)	01JULYYYY		
(E)	01JANYYYY		

In cases in the categories (A) and (E) when it is unclear due to the partial date if the AE started in SP1 or SP2 (YYYY = TRT2Y and MON=TRT2M in SP2) it will be considered to have started in SP2 and AE start date will be imputed as TRT2STD.

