2.3.2 Safety and tolerability assessments

2.3.2.1 AEs

An adverse event is the appearance or worsening of any undesirable sign, symptom, or medical condition occurring after starting the study drug even if the event is not considered to be related to study drug. Study drug includes the investigational drug under evaluation and the comparator drug that is given during any phase of the study. Medical conditions/diseases present before starting study drug are only considered adverse events if they worsen after starting study drug. Abnormal laboratory values or test results constitute adverse events only if they induce clinical signs or symptoms, are considered clinically significant, or require therapy.

Adverse events will be coded using MedDRA version 20.0.

Treatment emergent AEs (TEAEs) are events started after the first dose of study treatment and before study discontinuation or 30 days after last dose, whichever occurs later. In case where it is not possible to define an AE as TEAE or not, the AE will be classified by the worst case, i.e. treatment emergent.

All adverse events with start date on or after the date of the first study medication in SP2 will be counted as belonging to Study Period 2. In the case of a partial start date see [Appendix 1](#) on how such cases will be handled. If it is unclear whether the AE belongs to SP1 or SP2 then the AE will be assigned to SP2. This is a conservative approach since all patients are treated with the investigational product GP2017 in SP2.

Adverse events of special interest are defined as a subset of TEAE in [Appendix 3](#).

The investigator or qualified designee will have recorded ISRs belonging to one of the following: injection site erythema, injection site haematoma, injection site induration, injection site inflammation, injection site nodule, injection site oedema, injection site pain, injection site pruritus, injection site rash or injection site discolouration at the specified time points. Incidence and occurrence of ISRs and symptoms will be calculated.

All ISR are considered as a subgroup of TEAE. An ISR that fulfills the criteria of an SAE will be documented and reported as such.

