4.1.2 Study Period definitions

Day 1 of Study Period 1, i.e. the day on which the first dose of study medication is taken, is considered as the start for the SP1 and the study. All data before are considered belonging to Screening (SCR) period.

A patient is considered to have entered SP2 only if they have taken study medication assigned as belonging to SP2. The start of SP2 is defined as the first date of administration of study medication as assigned in SP2.

All data after study discontinuation (for AEs only in case they are after 30 days post last dose, see in Section 2.3.2.1) will be considered belonging to Follow-up (FUP) period. Concomitant medications started on day of discontinuation will be considered belonging to FUP period.

In cases where the last non-missing assessment and the start date coincide, the assessment will in general be considered pre-treatment (baseline), however AEs and medications commencing on the date of the first study medication injection will be considered post-baseline (SP1). Similarly, assessment on the day of the start date of SP2 will be assigned to SP1, while medications and AEs commencing on the day of the start date of SP2 will be assigned to SP2.

In the case of a partial date where it is unclear whether adverse events belong to SP1 or SP2 then they will be assigned to SP2. This is the more conservative assessment as all patients in SP2 are receiving the investigational product GP2017. Medications where it is unclear if they started in SP1 or SP2, i.e. there is a partial start date and no stop date in SP1, will be assigned to SP1 and reported in both periods.

Rules to impute partial dates for adverse events and concomitant medications for the purpose of assigning them to the correct study period are provided in [Appendix 1](#) and [Appendix 2](#). Completely missing dates will not be imputed.

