4.6.2.1 Adverse Event

AEs will be summarized by presenting the number and percentage of patients having any AE, by SOC and PT.

In addition, the number of events will also be presented for any AE, by primary SOC and for each PT. The average rate of adverse events will also be calculated as the number of events divided by the total number of years of exposure.

Missing and /or incomplete dates for AEs are imputed in a manner resulting in the earliest onset during the study period (see [Appendix 1](#) for details), additionally taking into account that the start date should not be after the stop date. The maximum of the earliest possible start date and the date of first administration of investigational study medication will be imputed for missing dates. If the end date is prior to the date of first administration of investigational study medication then the AE is not considered as a TEAE.

AE summary will be provided for all study periods by treatment groups and for the entire study separately. Following data will be summarized in the overall AE summary presentation.

Total number of TEAEs, patients with at least one TEAE, at least one SAE, at least one treatment related TEAE, at least one severe TEAE, at least one treatment related SAE, patients who discontinued the study due to TEAE, patients requiring study drug interruption and number of patients who died.

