6.2.2 Concomitant medication start date

This algorithm only applies to event that has partial start date. Please note that **completely missing start dates** will not be imputed.

Note: Imputed dates will be used in the derivation of prior medication or concomitant medication, and assignment of study periods. The actual partial dates will be reported in the listings. If the imputed concomitant medication (CMD) start date is after CMD end date, it will be set to CMD end date.

The following matrix explains the logic behind the imputation.

	MON MISSING	MON < TRTM	MON = TRTM	MON > TRTM
YYYY < TRTY	(D) Before Treatment Start	(A) Before Treatment Start	(A) Before Treatment Start	(A) Before Treatment Start
YYYY = TRTY	(C) Uncertain	(A) Before Treatment Start	(C) Uncertain	(B) After Treatment Start
YYYY > TRTY	(E) After Treatment Start	(B) After Treatment Start	(B) After Treatment Start	(B) After Treatment Start

The following table is the legend to the logic matrix.

	Day	Month	Year
Partial CMD Start Date	Not used	MON	YYYY
Treatment Start Date (TRTSTD)	Not used	TRTM	TRTY
Relationship			
Before Treatment Start	Partial date indicates CMD start date prior to Treatment Start Date		
After Treatment Start	Partial date indicates CMD start date after Treatment Start Date		
Uncertain	Partial date insufficient to determine relationship of CMD start date to Treatment Start Date		
Imputation Calculation			
NC / Blank	No convention		
(A)	15MONYYYY		
(B)	MAX (01MONYYYY, TRTSTD)		
(C)	TRTSTD		
(D)	01JULYYYY		
(E)	01JANYYYY		

According to this imputation, partial start dates during the treatment will be imputed with the earliest possible date, thus if from the partial date it is unclear if the medication started in SP1 or SP2 then it will be considered to have started in SP1. Note that when a partial start date clearly belongs to SP2 then the medication will be assigned to SP2 only.

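### SAP Appendix 1 puts year-only adverse events dated in the year of the first SP2 dose into SP1, although SAP 2.3.2.1 and 4.1.2 assign events of unclear period to SP2

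*SAP*

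**What the plan says.** SAP 2.3.2.1 sets the rule: "If it is unclear whether the AE belongs to SP1 or SP2 then the AE will be assigned to SP2". SAP 4.1.2 repeats it for partial dates, "where it is unclear whether adverse events belong to SP1 or SP2 then they will be assigned to SP2". Both give the same reason: everyone in SP2 receives GP2017, so SP2 is the conservative choice. Both point to Appendix 1 for the mechanics, and Appendix 1 says of its output: "Imputed dates will be used in the derivation of treatment emergent AEs and assignment of study periods".

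Appendix 1 (6.1.2) sorts partial start dates by comparing their year and month with those of the first dose (TRTSTD). Three categories matter here:

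- (A): month known, in or after the month of first dose. The start becomes the later of the first of that month and TRTSTD.
- (B): month missing, year equal to that of first dose. The start becomes TRTSTD.
- (E): month missing, year later than that of first dose. The start becomes 1 January of that year.

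An override follows. It begins "In cases in the categories (A) and (E) when it is unclear due to the partial date" and defines unclear by a test in brackets, "it is unclear due to the partial date if the AE started in SP1 or SP2 (YYYY = TRT2Y and MON=TRT2M in SP2": the year must equal TRT2Y and the month must equal TRT2M, the year and month of the first SP2 dose (TRT2STD). When the test is met, "it will be considered to have started in SP2 and AE start date will be imputed as TRT2STD".

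SAP 4.6.2.1 adds that AE dates are "imputed in a manner resulting in the earliest onset during the study period" and that a start should not fall after its stop. For medications, Appendix 2 states an explicit cap: "If the imputed concomitant medication (CMD) start date is after CMD end date, it will be set to CMD end date".

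**The concern.** A date with only a year leaves the study period most open, and the override does not reach it. In (E) the month is missing by definition, so a test that compares the month with TRT2M cannot be true. (B) is not named in the override. In both categories the default value stands, and it lies before the first SP2 dose with one calendar exception.

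The SP1 tables are the only randomized GP2017 versus Humira safety comparison, and the SP2 tables describe the switch. In a patient randomized to Humira, an AE that began after the switch, recorded only by a year that is also the year of the first SP2 dose, would be counted under Humira in SP1 and be absent from the switch evaluation. That is the reverse of the assignment that the SAP calls conservative.

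**Working it through.** The plan gives no figure to reproduce here, so the check applies the written algorithm to dates.

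**Inputs.** The categories and override are those of SAP 6.1.2. SP2 starts at its first dose (SAP 4.1.2). The planned Week 24 visit is Day 169 (Protocol Table 6-1), so the offset from first dose is 169 − 1 = 168 days. Using exactly 168 days for every patient is an assumption.

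**Worked dates, literal reading.**

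| First dose | First SP2 dose | AE start recorded | Category | Imputed start | Period given | Period under 2.3.2.1 and 4.1.2 |
|---|---|---|---|---|---|---|
| 10 Mar 2016 | 25 Aug 2016 | 2016 | (B) | 10 Mar 2016 | SP1 | SP2 |
| 10 Oct 2016 | 27 Mar 2017 | 2017 | (E) | 1 Jan 2017 | SP1 | SP2 |
| 10 Mar 2016 | 25 Aug 2016 | Aug 2016 | (A) | 25 Aug 2016 | SP2 | SP2 |
| 10 Mar 2016 | 25 Aug 2016 | 2017 | (E) | 1 Jan 2017 | SP2 | SP2 |
| 10 Oct 2016 | 27 Mar 2017 | 2016 | (B) | 10 Oct 2016 | SP1 | SP1 |

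Only the first two rows fail. The last two are not ambiguous between SP1 and SP2, because the whole recorded year lies on one side of the first SP2 dose.

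**All first-dose dates in a 365-day year.** Let d be the day of the year of the first dose. The first SP2 dose is in the same year when d + 168 ≤ 365, that is d ≤ 197. For a year-only AE dated in the year of the first SP2 dose:

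- d = 1 to 197 gives category (B): 197/365 = 54.0%, all to SP1.
- d = 198 to 365 gives category (E): 168/365 = 46.0%. At d = 198 the first SP2 dose is on 1 January and the AE goes to SP2. The other 167 go to SP1.
- In total, 197 + 167 = 364 of 365 first-dose dates give SP1.

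**Generous reading.** Suppose that naming (E) was meant to waive the month test there. Then all 168 (E) dates go to SP2, but the 197 (B) dates still go to SP1.

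**Comparison with Appendix 2.** For medications, a missing month is handled with the same two values, TRTSTD and 1 January. Appendix 2 itself says that taking the earliest possible date puts unclear cases in SP1, which is what 4.1.2 wants for medications. For AEs 4.1.2 wants the opposite.

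**Stop date.** Take an AE recorded as August 2016 with stop date 20 Aug 2016 and first SP2 dose 25 Aug 2016. Appendix 1 read alone imputes 25 Aug, after the stop. The constraint in SAP 4.6.2.1, applied as a cap, gives 20 Aug and SP1. Over all tested stop dates in the switch month before the first SP2 dose, Appendix 1 alone gave a start after the stop in 5373 of 5373 combinations, and the cap left none.

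**Scale.** One patient is 1/154 = 0.65 percentage points of a planned arm.

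**The case against.** The intent is clear. The governing rule stands twice in the body of the SAP, and the override names (E), so a careful programmer might waive the month test. Year-only start dates should be rare: AEs are sought at every visit and start dates are recorded. No AE is lost, because entire-study summaries are planned and listings show the partial dates as recorded. The rule treats both arms alike, so no differential bias is shown. The 54%/46% split describes first-dose dates under even recruitment, not affected AEs, and applies only to patients who enter SP2.

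These points limit the size, and they stand. They do not rescue the text: 6.1.2 is the algorithm to be programmed, and even the generous reading leaves (B) uncovered.

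Three stronger readings are tempting but not supported:

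- A reader might infer that the SAP lets AE starts fall after their stops. Appendix 1 alone would, but SAP 4.6.2.1, which cites Appendix 1, says the start should not be after the stop. What is missing is a statement in Appendix 1 of the value to impute, and that a stop before TRT2STD settles the AE as SP1.
- A reader might infer that overlooking the stop date is what sends AEs to SP1. It acts the other way: in month-known cases of category (A) it would push them to SP2.
- A reader might take the earliest-onset wording of 4.6.2.1 as a rival period rule. That is arguable: once an AE is assigned to SP2, TRT2STD is the earliest onset in that period, and the same paragraph goes on to treatment emergence.

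**Conclusion.** The defect is real and narrow. For patients who enter SP2, Appendix 1 assigns a year-only AE dated in the calendar year of the first SP2 dose to SP1, unless that dose is on 1 January. This contradicts SAP 2.3.2.1 and 4.1.2. It is an explicit rule with the wrong result, not a missing detail.

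It would be too broad to say that every post-switch AE with a year-only date is reported under Humira. This holds only for patients switched from Humira and only for AEs dated in the year of the first SP2 dose; a later year is correctly placed in SP2.

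The documents do not give the number of such AEs, and it is probably small. The effect is confined to the separate SP1 and SP2 safety summaries. Efficacy results and entire-study AE summaries are unaffected. The 54%/46% split between (B) and (E) rests on the 168-day offset and even recruitment over the year; the contradiction itself rests on neither. This is a worthwhile correction of low severity.

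**What to change.** In SAP 6.1.2, for patients who entered SP2, restate the override:

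- Category (A): impute TRT2STD when the year equals TRT2Y and the month equals TRT2M.
- Categories (B) and (E): impute TRT2STD when the month is missing and the year equals TRT2Y.
- Do not apply the override when the AE stop date is before TRT2STD; such an AE belongs to SP1.

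As a clarification, repeat in Appendix 1 the constraint already in SAP 4.6.2.1 by capping the imputed start at the stop date, as Appendix 2 does for medications.

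Under this rule the first two rows of the table move to SP2 and the other three do not change. In the August 2016 example with a stop on 20 Aug the override no longer fires: (A) gives the later of 1 Aug and 10 Mar 2016, that is 1 Aug 2016, in SP1 and before the stop.

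The cost is a few lines of SAP text and programming, with no new data.

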6.2 Appendix 2: Concomitant medication partial date imputation

6.2.1 Concomitant medication end date

- If the day is missing, then impute the last day of the month
- If the day and month are both missing, then impute the date with the day and month of the last available assessment date for the patient.
- If the end date is completely missing, the event will be assumed to be ‘Ongoing’

6.2.2 Concomitant medication start date

This algorithm only applies to event that has partial start date. Please note that **completely missing start dates** will not be imputed.

Note: Imputed dates will be used in the derivation of prior medication or concomitant medication, and assignment of study periods. The actual partial dates will be reported in the listings. If the imputed concomitant medication (CMD) start date is after CMD end date, it will be set to CMD end date.

The following matrix explains the logic behind the imputation.

	MON MISSING	MON < TRTM	MON = TRTM	MON > TRTM
YYYY < TRTY	(D) Before Treatment Start	(A) Before Treatment Start	(A) Before Treatment Start	(A) Before Treatment Start
YYYY = TRTY	(C) Uncertain	(A) Before Treatment Start	(C) Uncertain	(B) After Treatment Start
YYYY > TRTY	(E) After Treatment Start	(B) After Treatment Start	(B) After Treatment Start	(B) After Treatment Start

The following table is the legend to the logic matrix.

	Day	Month	Year
Partial CMD Start Date	Not used	MON	YYYY
Treatment Start Date (TRTSTD)	Not used	TRTM	TRTY
Relationship			
Before Treatment Start	Partial date indicates CMD start date prior to Treatment Start Date		
After Treatment Start	Partial date indicates CMD start date after Treatment Start Date		
Uncertain	Partial date insufficient to determine relationship of CMD start date to Treatment Start Date		
Imputation Calculation			
NC / Blank	No convention		
(A)	15MONYYYY		
(B)	MAX (01MONYYYY, TRTSTD)		
(C)	TRTSTD		
(D)	01JULYYYY		
(E)	01JANYYYY		

According to this imputation, partial start dates during the treatment will be imputed with the earliest possible date, thus if from the partial date it is unclear if the medication started in SP1 or SP2 then it will be considered to have started in SP1. Note that when a partial start date clearly belongs to SP2 then the medication will be assigned to SP2 only.

6.3 Appendix 3: Adverse events of special interest

- Infections
 - Tuberculous infections (HLT)
 - Atypical mycobacterial infections (HLT)
 - Pneumonia (PT)
 - Hepatitis B (PT)
 - Acute Hepatitis B (PT)
 - Hepatic viral infections (HLT)
 - Hepatitis C (PT)
 - Acute Hepatitis C (PT)
 - Sepsis, bacteraemia, viraemia and fungaemia NEC (HLT)
 - Listeriosis (PT)
 - Histoplasmosis (PT)
 - Legionella infection (PT)
 - Pneumonia legionella (PT)
 - Fungal infectious disorders (HLGT)
 - Pneumocystis infections (HLT)
 - Aspergillus infections (HLT)
 - Herpes viral infections (HLT)
 - Blastomycosis (HLT)
 - Coccidioidomycosis (HLT)
 - Arthritis bacterial (PT)
 - Erysipelas (PT)
 - Cellulitis (PT)
 - Diverticulitis (PT)
 - Pyelonephritis (PT)
- Malignancies
 - Neoplasms benign, malignant and unspecified (incl cysts and polyps) (SOC)
- Allergic reactions
 - Angioedema and urticaria (HLGT)
 - Urticaria (PT)
 - Hypersensitivity (PT)
 - Anaphylactic reaction (PT)
 - Drug hypersensitivity (PT)
 - Allergic Bronchospasm (PT)
- Immune system disorders/Autoimmune events
 - Acute and chronic sarcoidosis (HLT)
 - Vasculitides (HLT)

- Vasculitides NEC (HLT)
- Autoimmune pancytopenia (PT)
- Autoimmune hepatitis (PT)
- Autoantibody positive (PT)
- Lupus-like syndrome (PT)
- Interstitial lung disease (PT)
- Neurological events
 - Demyelinating disorders
 - Multiple sclerosis (PT)
 - Optic neuritis (PT)
 - Guillain-Barre syndrome (PT)
- Hematological reactions
 - Pancytopenia (PT)
 - Thrombocytopenia (PT)
 - Anaemia (PT)
 - Aplastic Anaemia (PT)
 - Leukopenia (PT)
 - Neutropenia (PT)
 - White blood cell count decreased (PT)
 - Agranulocytosis (PT)
 - Leukocytosis (PT)
 - Idiopathic thrombocytopenic purpura (PT)
- Congestive Heart Failure
 - Cardiac failure congestive (PT)
 - Hypertension (PT)
 - Arrhythmia (PT)
- Gastrointestinal disorders
 - Gastrointestinal haemorrhage (PT)
 - Pancreatitis (PT)
 - Intestinal perforation (PT)
- Hepato-biliary disorders
 - Hepatic enzyme increased (PT)
 - Cholecystitis (PT)
 - Cholelithiasis (PT)
 - Hepatic steatosis (PT)
 - Hepatic failure (PT)
- Renal and urinary disorders
 - Renal impairment (PT)

- Respiratory, thoracic and mediastinal disorders
 - Asthma (PT)
 - Interstitial lung disease (PT)
 - Pulmonary embolism (PT)
 - Pleural effusion (PT)
 - Pulmonary fibrosis (PT)

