## **5.5.9      Study drug discontinuation and premature patient withdrawal**

### **Study drug discontinuation**

Patients may voluntarily discontinue study treatment for any reason at any time. The investigator should discontinue study treatment for a given patient if, based on benefit/risk assessment, he/she believes that continuation would not be favorable to the patient's well-being or if a patient did not improve (did not achieve the treatment target) or the disease activity deteriorated compared to previous DAS28-CRP score.

Study treatment must be discontinued under the following circumstances:

- Withdrawal of informed consent

- Violation of methods of contraception as described in Section [6.5.7](#)
- Emergence of the following AEs:
  - Any severe or serious AE that is not compatible with the administration of study drug
  - In case of a serious infection or sepsis
  - Severe heart failure (NYHA class III or IV), or other severe, uncontrolled cardiovascular disease
  - Uncontrolled hypersensitivity to study medication
  - Any persisting laboratory abnormalities that in the judgement of the investigator, taking into consideration the patient's overall status, prevents the patient from continuing participation in the study
  - Hepatitis B virus (HBV) infection. Should a patient develop HBV infection during the study, the study medication should be discontinued and should not be re-started, even after the infection is controlled or resolved. MTX should also be discontinued until the HBV infection is controlled or resolved.
  - Occurrence of any signs or symptoms of tuberculosis or suspicion of tuberculosis (per the investigator's discretion) during study course will lead to discontinuation of study drug and the patient will be withdrawn from the study
  - Malignancy, except for basal cell carcinoma
- Pregnancy
- Use of the prohibited medications as described in Section [5.5.8](#)
- Any other protocol deviation that results in a significant risk to the patient's safety
- Non-responders at Week 24
- Emergency unblinding

The date and primary reason for stopping study treatment should be recorded in the eCRF (e.g. Study Drug Discontinuation Form).

See Section [6](#) for the required assessments of these patients after study drug discontinuation.

The investigator must also notify the IRT system of the study drug discontinuation.

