## 7.2 Serious adverse events

### 7.2.1 Definition of SAE

An SAE is defined as any adverse event (appearance of or worsening of any pre-existing undesirable sign(s), symptom(s) or medical conditions(s)), which meets any one of the following criteria:

- is fatal or life-threatening
- results in persistent or significant disability/incapacity
- constitutes a congenital anomaly/birth defect
- requires inpatient hospitalization or prolongation of existing hospitalization, unless hospitalization is for:
  - routine treatment or monitoring of the studied indication, not associated with any deterioration in condition (specify what this includes)
  - elective or pre-planned treatment for a pre-existing condition that is unrelated to the indication under study and has not worsened since the start of study drug
  - treatment on an emergency outpatient basis for an event not fulfilling any of the definitions of a SAE given above and not resulting in hospital admission
  - social reasons and respite care in the absence of any deterioration in the patient's general condition
- is medically significant, i.e. defined as an event that jeopardizes the patient or may require medical or surgical intervention to prevent one of the outcomes listed above

Life-threatening in the context of a SAE refers to a reaction in which the patient was at risk of death at the time of the reaction; it does not refer to a reaction that hypothetically might have caused death if more severe (see Annex IV, ICH-E2D Guideline).

All malignant neoplasms will be assessed as serious under "medically significant" if other seriousness criteria are not met.

Any suspected transmission via a medicinal product of an infectious agent is also considered a serious adverse reaction.

Medical and scientific judgment should be exercised in deciding whether other situations should be considered serious reactions, such as important medical events that might not be immediately life threatening or result in death or hospitalization but might jeopardize the patient or might require intervention to prevent one of the other outcomes listed above. Examples of such events are intensive treatment in an emergency room or at home for allergic bronchospasm, blood dyscrasias or convulsions that do not result in hospitalization.

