4.6.2.1.3 Summary of AEs of special interest

Selected AEs, considered under the heading of potential and identified risks will be presented under summary of AEs of special interest. Definition of an AE as an AE of special interest is given in [Appendix 3](#).

In addition separate summaries will be provided for death, serious AEs (SAEs), other significant AEs leading to discontinuation by treatment group and overall.

These summaries will be presented separately for all study periods by treatment group and overall.

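### Two special-interest event groups in SAP Appendix 3 (Malignancies, Congestive Heart Failure) count events other than the risk they name, and no group isolates serious infections

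*SAP*

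**What the plan says.** SAP 4.6.2.1.3 gives the purpose of the summary: "Selected AEs, considered under the heading of potential and identified risks will be presented under summary of AEs of special interest". It is to be produced for each study period, by treatment group and overall. SAP 2.3.2.1 makes these events a subset of treatment-emergent events and refers to Appendix 3 for the definition.

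Appendix 3 (SAP 6.3) lists eleven groups. Three matter here.

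- *Malignancies* has a single entry, a whole MedDRA system organ class: "Neoplasms benign, malignant and unspecified (incl cysts and polyps) (SOC".
- *Congestive Heart Failure* has three preferred terms: "Cardiac failure congestive (PT", "Hypertension (PT" and "Arrhythmia (PT".
- *Infections* has 24 entries at various MedDRA levels. Some are normally serious, for example "Sepsis, bacteraemia, viraemia and fungaemia NEC (HLT". Others are broad classes taken at any severity, such as all fungal and all herpes viral infections.

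Neither the appendix nor the two SAP sections that point to it adds a seriousness criterion. The SAP does not say whether the table shows group totals, preferred terms or both.

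The protocol uses narrower wording for the same risks. Section 5.5.9 names malignancy (with basal cell carcinoma excepted), severe heart failure by NYHA class together with other severe uncontrolled cardiovascular disease, and "In case of a serious infection or sepsis". Section 7.2.1 adds: "All malignant neoplasms will be assessed as serious".

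**The concern.** Readers take a row label at face value. A row headed *Malignancies* that includes colon polyps and cysts does not report malignancies, and a row headed *Congestive Heart Failure* that includes raised blood pressure does not report heart failure. Both are rare risks, while the added terms may well be more frequent, so the added terms could supply most of a group total.

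The error can run in either direction. Background events in both arms can make a real imbalance harder to see. A chance imbalance in hypertension or benign lesions can look like a cardiac or cancer signal in one arm or after the switch.

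The infection group has a different weakness. The protocol frames that risk by seriousness, but the group is framed by type of infection. It therefore gives no direct count of serious infections by arm.

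**Working it through.** The plan states no rate or power for these groups, so there is no figure to reproduce. The check compares labels with contents, followed by an illustration of scale.

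**Label against content**

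| Group | Entries | What is counted | Match with label |
|---|---|---|---|
| Malignancies | 1 (whole class) | malignant, unspecified and benign neoplasms, cysts, polyps | over-inclusive |
| Congestive Heart Failure | 3 preferred terms | heart failure (1), hypertension (1), arrhythmia (1) | 1 of 3 terms |
| Infections | 24 | listed types at any seriousness | label fits, but serious events are not isolated |

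The protocol itself separates polyps from cancer: exclusion criterion 13 bars a history of cancer but admits patients whose non-invasive colon polyps were removed. A new polyp during the trial would nevertheless be counted under *Malignancies*.

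For infections, a serious event coded to a term outside the 24 entries (for example a lower respiratory infection not coded as pneumonia, or a urinary infection not coded as pyelonephritis) is not of special interest. A non-serious herpes or fungal infection is.

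**Where else the events appear**

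- Protocol 9.5.3 tabulates treatment-emergent events, serious events, events leading to premature discontinuation and deaths by system organ class and preferred term.
- SAP 4.6.2.1 gives patients and events by class and term, and a rate per year of exposure.
- SAP 4.6.2.1.3 adds separate summaries of deaths, serious events and events leading to discontinuation.

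Because every malignant neoplasm is classed as serious, each one appears by term in the table of serious events. Serious infections appear there under their class. Congestive cardiac failure has its own preferred-term line in the general table.

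**Scale, on assumed rates**

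Inputs: 154 patients per arm (protocol 5.2). Assumed incidence p for the named risk is 0.2% to 1%, and q for the other terms in the group is 1% to 5%, taken as independent.

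Proportion of patients in the group = 1 − (1 − p)(1 − q). Share with the named risk = p divided by that proportion.

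| p | q | Named risk, patients per arm | Whole group, patients per arm | Share with named risk |
|---|---|---|---|---|
| 0.2% | 1% | 0.31 | 1.84 | 17% |
| 0.2% | 5% | 0.31 | 7.99 | 4% |
| 1% | 1% | 1.54 | 3.06 | 50% |
| 1% | 5% | 1.54 | 9.16 | 17% |

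For example, with p = 0.2% and q = 5%: 1 − 0.998 × 0.95 = 0.0519; 154 × 0.0519 = 7.99; 0.002 / 0.0519 = 4%.

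**Direction, on invented counts**

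- Three heart failures against none, plus 5 hypertension cases in each arm, reads 8 v 5. The absolute difference is still 3 patients (3 / 154 = 1.9 percentage points), but the ratio becomes 8 / 5 = 1.6 and the all-or-none contrast disappears.
- No heart failure in either arm, with hypertension by chance at the two ends of an assumed 2–5% range (154 × 2% = 3.1 and 154 × 5% = 7.7), reads about 8 v 3 under a heart-failure label.

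**The case against.** The strongest reply is that nothing is lost. The other tables show malignancies, serious infections and cardiac failure by arm at class and term level. That stands, and it limits the point to presentation. It does not repair a mislabelled row in the table that the SAP sets aside for identified and potential risks.

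A broad class can also serve as a sensitive screen, and hypertension and arrhythmia may have been placed with heart failure deliberately as cardiovascular risks. The documents do not include the source of the risk list, so this cannot be excluded. If that was the intention, the label should say so. It is also fair that protocol 5.5.9 is a list of reasons to stop treatment, not a definition of special-interest events; it is used here only to show how the protocol words these risks.

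Three stronger readings are tempting, and the documents do not support them.

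- A reader might infer that serious infection goes uncaptured, or that Appendix 3 is the only rule for tabulating these risks. The list includes sepsis, tuberculosis, pneumonia and opportunistic infections, and the table of serious events covers the rest.
- A reader might infer that the groupings fail in general. The mismatch between label and content is shown for two of eleven groups, and both over-include; neither drops the entry that carries its named risk.
- A reader might infer a bias towards similarity. Adding equal background counts leaves the absolute difference unchanged, unequal ones can create a false signal, and the safety output is descriptive, with no margin or test.

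**Conclusion.** The point holds in limited form. Two labels, *Malignancies* and *Congestive Heart Failure*, do not match their listed terms, so any group total under them misstates the named risk by arm and period. Separately, no group is defined by seriousness, so no special-interest row shows serious infections.

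The mismatch follows directly from the text and needs no assumption. Its size does: the 4–50% share rests entirely on the assumed incidences, and the 3 v 0 example lies above what those rates would lead one to expect (at most 1.54 patients per arm). The practical effect also depends on the table layout. If only group totals are shown it is at its largest; if preferred terms are shown beneath, much of it can be undone by the reader.

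The effect is confined to descriptive safety output. The primary and key secondary analyses are untouched.

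**What to change.** Amend SAP Appendix 3, with the term lists fixed before unblinding:

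1. Under *Malignancies*, report malignant and unspecified neoplasms, with unspecified as its own sub-row. Put benign neoplasms, cysts and polyps in a separate row. The sub-row matters because the automatic seriousness rule in protocol 7.2.1 covers only malignant neoplasms; an unspecified one left out of both rows might not be picked up by the table of serious events.
2. Take hypertension and arrhythmia out of *Congestive Heart Failure* and show each in its own row.
3. Keep the infections list and add a *Serious infections* row: treatment-emergent events in the infections class that are flagged serious.
4. State in SAP 4.6.2.1.3 that the table shows both group totals and preferred terms.

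No new data are needed. Protocol 7.1 already records seriousness for every adverse event, and MedDRA coding is already planned. The cost is a few lines of SAP text and programming, and a slightly longer table. The SAP says it will be finalised before database lock and unblinding, so the lists can be set without sight of results by arm.
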